 - b. [Study Setting](#)
 - c. [Inclusion/Exclusion criteria](#)
 - d. [Recruitment](#)
3. [Outcome Measures](#)
4. [Risk and Benefit estimates](#)
 - a. Assessment of Safety
 - b. Adverse events
5. [Statistical Analysis](#)
6. [Research Protocols](#)
7. [Data Collection forms](#)
8. [Confidentiality](#)
9. [Timeline](#)
10. **Appendices**
 - a. Appendix 1: [Nerve block protocol](#)
 - b. Appendix 2: [Multi-modal perioperative management protocol](#)
 - c. Appendix 3: [MME equivalence](#)
 - d. Appendix 4: [PACU and SDC Discharge criteria](#)
 - e. Appendix 5: [Study Timeline](#)

SECTION 1: INTRODUCTION ([back](#))

Background/Justification

Breast cancer is the most commonly diagnosed cancer in females in Canada, making up 25% of all cancers diagnosed in this population.¹ When surgical treatment necessitates a mastectomy, immediate breast reconstruction (IBR) is a safe option for patients with early stage cancer.² Options for breast reconstruction include autologous tissue or alloplastic reconstruction with a prosthesis (insertion of tissue expander or immediate insertion of implant). In Canada, rates of IBR are increasing, with approximately 15-40% of breast cancer patients undergoing reconstruction in British Columbia.³ Alloplastic reconstruction (with tissue expanders and implants) accounts for the majority of reconstructions in North America and is associated with more pain than autologous forms of breast reconstruction.⁴⁻⁹

Importantly, acute and chronic pain can be a major factor in patient recovery after breast reconstruction surgery.¹⁰ Approximately 40%-47% of patients undergoing breast surgery experience significant acute postoperative pain.^{5,11} Severe acute postoperative pain increases the likelihood of chronic pain in the breast and ipsilateral arm.¹² Chronic postoperative pain, defined as pain that persists after 3-6 months after surgical intervention, hinders survivor recovery, reducing productivity and overall quality of life.^{13,14} One year after surgery, approximately 50% of patients who had a mastectomy and reconstruction experience pain compared to 30% of women who had a mastectomy without reconstruction.^{5,15-17} Recent population cohort studies report little improvement in the incidence of chronic post-mastectomy pain, estimating 40-50% of patients suffer with resultant decrease in quality of life.^{12,16,17}

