Disadvantages of the TPVB includes poor anesthesia of the medial anterior chest and operator dependence, potentially influencing the efficacy and safety of the block.

Selecting the optimal regional block for Alloplastic Breast Reconstruction

There is growing evidence to support the addition of pecs I and SA blocks for mastectomy (with or without axillary surgery) with IBR using tissue expanders or immediate implants. Early case reports and subsequent series in breast surgery with and without reconstruction supported the combination of Pecs I and SA blocks resulting in lower opioid consumption.⁵³⁻⁵⁶ A single RCT of combined Pecs I and SA blocks for modified radical mastectomy with axillary lymph node dissection and IBR reported reduced opioid consumption and decreased postoperative pain scores.⁵⁷ While promising, this trial did not specify the type of breast reconstruction performed.

Two RCTs found the Pecs II block resulted in improved postoperative analgesia and reduced opioid consumption compared to TPVB.^{58,59} However, meta-analyses of 14 randomized trials comparing Pecs II and TPVB concluded that Pecs II and TPVB provide comparable analgesic effect.⁶⁰ Although Pecs II has merit, the disruption of axillary tissue as a result of Pecs II renders this regional block an inferior option for our surgical population which commonly requires sentinel lymph node biopsy or axillary dissection.³⁸

There is a paucity of high-quality studies investigating the additional benefit of regional blocks for immediate breast reconstruction. Given the effectiveness and safety of TPVB, Pecs I and SA blocks in oncologic breast surgery, we sought to investigate the benefit of TPVB with Pecs I block in the framework of a multimodal peri-operative management protocol. We have selected the most effective block in oncologic breast surgery, namely TPVB, and added the Pecs I (TPVB+) to provide the anesthesia required for the disruption of pectoralis muscle that occurs with immediate alloplastic breast reconstruction.

Hypothesis [\(back\)](#)

Local anesthetic regional blocks (LA blocks) of the thoracic paravertebral space and the pectoralis major (TPVB+) will reduce chronic pain.

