On the day of surgery, the regional anesthesiologist at MSJH will be provided with the Study ID specific sealed envelope which will assign the patient to receive either the LA block or sham block. The regional anesthesiologist will prepare local anesthetic or normal saline injections for infiltration based on the random assignment. For all patients, the regional block will be performed as outlined in the Procedure Protocols (See Appendix 1: Nerve Block). The regional anesthesiologist will be unblinded and will therefore be able to purposefully inject the saline block in a safe plane outside of the paravertebral space to further reduce the risk of pneumothorax. All other parameters and protocols will be identical.

Currently, at MSJH, approximately 4 - 5 cases of mastectomy with IBR are performed per week. We do not anticipate difficulty with enrolment into this study. This internal pilot will generate initial recruitment data to enable an early review and validation of our recruitment projections and study population target prior to transition to formal RCT.

Study Setting [\(back\)](#)

The pilot trial will take place at MSJH in Vancouver, BC. Study enrolment and all subsequent study activities will take place on site at MSJH. The planned timeline for recruitment into the study is one year from REB approval (tentatively December 2020).

Inclusion Criteria [\(back\)](#)

- 1- Patients must be female, and at least 19 years old.
- 2- Patients must be ASA grade I or II.
- 3- Patients must be undergoing total mastectomy with IBR using tissue expander or implant, with or without axillary surgery.

Exclusion Criteria [\(back\)](#)

Patients will be excluded if:

- 1- Patients have a known contraindication for a regional block: known coagulation disorder, treatment with anticoagulants, infection at the injection site, known allergy to medication in the study.
- 2- Patients who are pregnant at the time of surgery.
- 3- Patients having bilateral mastectomy and immediate alloplastic breast reconstruction (as only one side can be blocked to prevent local anesthesia toxicity).
- 4- Patients with ASA Class III or IV.
- 5- Patients with BMI > 35 kg/m².
- 6- Patients weighing less than 50 kg.
- 7- Patients living/staying outside of 1-hour driving distance from hospital.

Recruitment [\(back\)](#)

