Preliminary evidence of efficacy: Although severe acute post-operative pain is not the only risk factor for chronic post-surgical pain (CPSP), an intervention that does not decrease postoperative pain is unlikely to have a significant impact on CPSP. If the 80%

confidence interval for the between-group difference in average pain score in the 24-hour postoperative period favours LA block, we will consider that preliminary evidence of efficacy.^{65,66}

Secondary outcomes of the pilot trial include adverse events related to study interventions. We will also collect the outcomes for the definitive trial to test and refine data collection processes.

The primary outcome in the definitive trial is chronic pain, defined by the Pain Burden Index, measured at 3 and 6 months following surgery. The Pain burden Index examines postsurgical pain in four postoperative body areas. The Index is calculated as a sum of the four locations (breast, chest, axilla, arm) multiplied by the frequency of pain¹² (see Form 8: Pain Burden Index).

Secondary outcomes of the definitive trial include:

- Opioid analgesia requirements during surgery and in the first 24 hours after surgery, defined as morphine milligram equivalents (MME). The total MME will include intraoperative opioids administered in the OR and postoperative opioids administered/ingested in the Postanesthetic Care Unit (PACU), Surgical Day Care Unit (SDC), Inpatient Unit, and home in the 24-hour period after completion of surgery. Opioids consumed will be converted to MME (see Appendix 3: Calculation of Morphine Milligram Equivalents (MME)).
- Acute patient-reported pain scores:
 - Numerical Rating Scale (NRS; 11-point scale) measured at the standard time points of nursing care assessments: preoperatively (baseline); four times per hour in PACU until discharge; if admitted, hourly for 2 hours, and then every 6 hours in the Inpatient Unit; and at discharge from hospital; 24 hours after surgery is complete.
- Opioid-induced side effects:
 - Postoperative nausea and vomiting
 - Nausea severity (by Verbal Rating Scale) in PACU
 - Vomiting episodes (0-48 hours after surgery) in PACU & home
- Quality of recovery (Form 7: Quality of Recovery-15 Questionnaire)

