24 hour time point will be marked on the QoR-15 form. If paper format is preferred, the QoR-15 will be provided with a paid-postage envelope to return once completed at 24 hours after surgery. The pain NRS at 24 hours will be recorded from the chart. The envelopes will be addressed to the research coordinator at UBC Hospital office. If the participant prefers electronic format, the questionnaire will be sent to their provided email address using secure online format (REDCap developed questionnaire).

Recovery Booklet (see Form 5) will include: a) schedule for taking prescription pain medications; b) a postoperative 7-day symptom diary (for recording pain on NRS at 24 hours, episodes of vomiting, nausea, and use of prescribed medications). Patients will be provided with a paid-postage envelope to return their Recovery Booklet via mail once completed at 7 days after surgery. Patients will be reminded to complete the Recovery Booklet (Form 5) in 3-4 days and once again at 14 days to return the envelope.

The Pain Burden Index questionnaire (see Form 8) asks specifically about pain in four surgically related body areas and to calculate the Pain Burden Index (PBI). The PBI is calculated by summing the pain severity scale (0–10) at each of four locations (breast, axilla, chest wall, arm) multiplied by the frequency of the pain at each site. The PBI questionnaire will be sent to participants via mail as paper format (with paid-postage envelope to return once completed) or email as electronic format (as per their requested preference) to be completed 3 and 6 months after their surgery. Details of present adjuvant treatments (radiation and chemotherapy) will also be included in the questionnaire.

Secondary outcomes data including opioid consumption and side effects, length of stay in hospital (hours), rescue medications, failure of early discharge, complications and adverse events and time-based outcome measures (time in PACU, time under general anesthesia, time to perform ultrasound-guided TPVB+, failure of discharge from PACU and requiring admission) will be collected through participants' charts and EMR.

Risk/Benefit Estimates [\(back\)](#)

Anticipated Benefits to Participants

Participants will be randomly assigned to receive TPVB+ nerve blocks with either local anesthetic or sham (saline) followed by general anesthesia.

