Participants will be randomly assigned to receive TPVB+ with local anesthetic or sham before general anesthesia. For all participants, data will be collected on the Intake Form, Clinical Form, Quality of Recovery-15 Questionnaire, Pain Burden Index, and Recovery Booklet in the following 7 sections:

1. The Intake Form will be completed by the patient during the initial contact phone call and includes information on general demographics and inclusion/exclusion criteria (without identifying information).
2. The first section of the Clinical Form will be used to record information on the perioperative course including the type of surgery performed: unilateral or bilateral; partial or total mastectomy with or without sentinel lymph node biopsy or axillary lymph node dissection; tissue expander or immediate implant reconstruction; adjunctive procedures will be recorded including biopsies and balancing reduction procedures.
3. The second section of the Clinical Form will record information on the general anesthesia provided; preoperative medications, intraoperative analgesics, sedatives, antiemetics, and anxiolytics. The form will also include details on the regional block and time to perform the block. Surgical and regional block complications within 24 hours of surgery will be recorded.
4. The third section of the Clinical Form will include information on participant-reported pain scores and medications in the postanesthetic care unit and inpatient ward.

5. The Quality of Recovery-15 Questionnaire will be completed by the participant at baseline before surgery and at 24 hours after surgery to evaluate the quality of their recovery.
6. The Recovery Booklet will be completed by the participant during the first 7 days after surgery to track scheduled and rescue medications required, opioid-related side effects (nausea and vomiting), and pain at 24 hours after surgery.
7. The Pain Burden Index will be completed by the participant 3 months and 6 months after surgery to evaluate for the presence and severity of chronic pain.

Confidentiality [\(back\)](#)

Management of Identifying Data:

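### The Pain Burden Index, the definitive trial's primary outcome, has no preoperative value and existing pain is not excluded, so prior pain may score as chronic postsurgical pain

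*Protocol*

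**What the plan says.** The Hypothesis section states that the block "will reduce chronic pain". Outcome Measures fixes the endpoint: "The primary outcome in the definitive trial is chronic pain, defined by the Pain Burden Index, measured at 3 and 6 months following surgery". It describes the instrument thus: "The Pain burden Index examines postsurgical pain in four postoperative body areas". Additional Details of Study Design gives the score as severity (0–10) times frequency, summed over breast, axilla, chest wall and arm, with the questionnaire "to be completed 3 and 6 months after their surgery". Data Collection, item 7, repeats the timing: "The Pain Burden Index will be completed by the participant 3 months and 6 months after surgery". The Confidentiality section gives the same two time points.

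Background describes the target condition: "Chronic postoperative pain, defined as pain that persists after 3-6 months after surgical intervention". This sets a duration but does not require that the pain be new or worse than before.

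The first exclusion criterion covers block contraindications: "known coagulation disorder, treatment with anticoagulants, infection at the injection site, known allergy to medication in the study". The other six concern pregnancy, bilateral reconstruction, ASA class, BMI, low weight and distance from the hospital.

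Before surgery, patients complete Form 4, which holds the Intake Form and a baseline QoR-15. A preoperative numerical pain rating is also taken.

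**The concern.** A block given before incision is meant to prevent pain caused by the operation. It is not expected to remove arm or chest pain that the patient already had. With no baseline index, no exclusion for prior pain and no onset rule in the protocol text, a patient with unchanged arm pain from before surgery could receive the same 6-month score as a patient whose arm pain began with surgery.

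Three things would be lost. Some cases counted against the block could not have been prevented. The comparison could not be adjusted for the patient's own starting value. Chance differences in prior pain between arms could be neither seen on this scale nor corrected.

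A statistical analysis plan can choose a model later, but it cannot recover a preoperative value that was never collected. The pilot is the place to act: Study Design says it shares the definitive trial's design, and Outcome Measures says the definitive outcomes are collected in it to try out and improve data collection.

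**Working it through.** **1. Schedule of the index.** Outcome Measures, Additional Details of Study Design, Data Collection (item 7) and Confidentiality all give 3 and 6 months, and nothing before surgery. Form 8 is handed out in the post operative package.

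**2. Baseline pain information that is planned.** There is one preoperative 0–10 rating, and a baseline QoR-15 that includes pain among its domains. Neither is described as recording site or frequency, so neither can be turned into a baseline index. The Intake Form is described as covering demographics and eligibility.

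**3. The protocol's own sample size.** Inputs from Outcome Measures: 50% against 30%, two-sided alpha 0.05, beta 0.15. Allocation is 1:1 (Study Design).

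n per arm = [1.960 × √(2 × 0.40 × 0.60) + 1.036 × √(0.50 × 0.50 + 0.30 × 0.70)]² / 0.20² = (1.358 + 0.703)² / 0.04 ≈ 106.2, so 107 per arm and 214 in total.

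This agrees with the stated figure of about 220. At 110 per arm the power is Φ[(0.20 × √110 − 1.358) / 0.678] = Φ(1.09) = 86%.

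**4. Illustration of dilution.** The documents give no share q of patients with prior pain at these sites, so q is assumed. Suppose 50% and 30% are rates of new pain, and the prior pain persists whatever the arm. The observed rate is then q + (1 − q) × p, that is 0.5 + 0.5q against 0.3 + 0.7q. With the same power formula:

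| Assumed q | Observed rates | Difference | Power at 220 | Total N for 85% |
|---|---|---|---|---|
| 0 | 50% vs 30% | 20 points | 86% | 214 |
| 10% | 55% vs 37% | 18 points | 77% | 274 |
| 20% | 60% vs 44% | 16 points | 66% | 348 |

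**5. How far this depends on the reading of 50% and 30%.** If both are rates of the outcome as it will be measured, prior pain included, nothing is lost and power stays at 86%. If the 50% already includes q and the relative risk of 0.30 / 0.50 = 0.6 acts only on the rest, the block arm has q + 0.6 × (0.5 − q). That is 34% at q = 10% (power 67%) and 38% at q = 20% (power 43%). The protocol does not say which reading it intends.

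**6. Chance imbalance.** The standard deviation of the between-arm difference in prior-pain share is √(2q(1 − q)/n). For q of 10% to 20% this is 11 to 15 percentage points at 15 per arm, and 4 to 5 points at 110 per arm. Its expected value is zero.

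**The case against.** The strongest reply is that the instrument itself is not in view. The protocol calls it a measure of postsurgical pain, and Form 8 may ask only about pain since the operation. This stands: a reader might infer that prior pain is certainly counted, but the documents support only that it may be.

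Some baseline pain information exists, and a plan that is not shown could use it. That is so, but these measures can flag patients with prior pain without giving a value by site and frequency.

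A reader might also infer that the comparison is biased. It is not: allocation is randomised and patients report under blinding, so prior pain is balanced on average.

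A reader might infer that 220 patients are too few. The documents do not show this. Background cites about 50% as the share of patients in pain one year after mastectomy with reconstruction, without calling it new pain. Adding prior pain on top may therefore count it twice.

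Nor can a baseline index be called the best available covariate. Background lists predictors of chronic pain after breast surgery and preoperative pain is not among them.

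Finally, the pilot's decisions rest on enrolment, block success, retention and the 80% confidence interval for 24-hour pain. None of these uses the index. Study Design calls this an internal pilot, while Outcome Measures places it ahead of a definitive multi-centre trial, and no section says that pilot index data will be pooled. The permanent loss may therefore be confined to about 30 patients, provided the gap is closed before the definitive trial.

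**Conclusion.** The point holds as a cheap design improvement, not as an error or contradiction. The definitive trial's primary outcome has no baseline measurement, patients with pain at the scored sites are eligible, and the text has no rule separating new from prior pain. Unless Form 8 supplies one, prior pain may score as chronic postsurgical pain.

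The consequence is dilution and lost precision, not systematic bias between arms. The documents do not allow its size to be fixed. The fall in power from about 86% to 77% or 66% is an illustration that assumes 10% or 20% of patients have unmodifiable prior pain and that 50% and 30% refer to new pain. Under other readings the loss is nil or larger. The stated 220 is arithmetically sound, and the pilot's progression criteria are unaffected.

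**What to change.** Add one preoperative completion of the Pain Burden Index to Form 4, alongside the baseline QoR-15, starting in the pilot. State that the 3- and 6-month index comparison will be adjusted for the baseline value. Check the wording of Form 8 and state in the protocol whether it asks about all current pain or only pain since surgery.

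Report pain that is new or worse than baseline as a supportive summary only. Making it the primary endpoint would change what is being estimated, and the 50% and 30% planning rates would have to be re-based.

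The cost is one short questionnaire (four sites, severity and frequency) in a package patients already complete, the matching REDCap fields and a minor ethics amendment. The downside is slightly more baseline burden for patients. No treatment, visit or eligibility rule changes.

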Appendix 1: Nerve Block Protocol: TPVB+ (TPVB with Pec I block) [\(back\)](#)

All sham and LA blocks will be performed by a regional anesthesiologist experienced in performing TPVB and Pec I blocks. The blocks will be performed in the preoperative block room. Participants will be monitored as per existing site policy. The blocks will be done using sterile technique. Before and after each procedure, the ultrasound machine will be cleaned and disinfected using disinfectant wipes and allowed to air dry as per hospital/site policy.

1. Prior to the procedure, the patient will have the procedure explained to them, and consent documented as per hospital policy. Standard monitors and a safety check will be performed. Sedation medication (midazolam 1-2mg and fentanyl 25-50mcg) will be given.
2. The regional anesthesiologist will prepare syringes for injection of sham and regional anesthetic blocks depending on patient allocation.
3. Syringes for injection may include:
 - a. LA TPVB block: 25ml of 0.3% ropivacaine with 1:400K epinephrine
 - b. LA Pecs I block: 10ml of 0.3% ropivacaine with 1:400K epinephrine
 - c. Sham TPVB block: 25ml normal saline (0.9% NaCl)
 - d. Sham Pecs I block: 10ml normal saline (0.9% NaCl)
4. The skin at the planned injection site will be cleansed with 2% chlorhexidine solution or 1% iodine (10% povidone iodine) in case of chlorhexidine allergy.
5. Nonsterile conducting gel will be applied to the 9 MHz linear probe ultrasound transducer, and the transducer will be covered with a sterile drape.
6. The anesthesiologist will don a clean face mask and sterile gloves prior to handling sterile equipment or touching the sterile field.
7. Sterile ultrasound conducting gel will be applied to the skin.
8. Local anesthetic skin wheal will be raised with 1% lidocaine.
9. TPVB block: The T2/3 or 3/4 interspace will be determined by counting ribs with the ultrasound. The ultrasound probe will be placed in a sagittal orientation aiming to visualize the transverse processes. The location of the pleura will be noted and the LA will be injected in the paravertebral space incrementally after negative aspiration looking for pleural drift. For the sham injection the needle will be inserted to just superficial to the transverse process for an erector spinae plane injection (between erector spinae muscles and the transverse processes).
10. Pecs I block: Infiltrate will be injected into the fascia between the pectoralis minor and pectoralis major muscles at the level of the 3rd rib in the mid-to-lateral 1/3 of the clavicle in a transverse to oblique orientation. Identification of the pectoral branch of the thoracoacromial artery will assist with needle placement. The needle will be inserted from medial/superior to lateral/inferior. Visual confirmation will be by ultrasound upon visualizing the separation of tissue layers with the injected infiltrate.
11. The needle and probe will be removed and the injection site wiped dry.
12. The patient will be continuously monitored in the block area until ready for transport to the operating room for surgery.

Appendix 2: Evidenced-Based Multimodal Perioperative Analgesia and Anti-emetic Management Protocol for Alloplastic Immediate Breast Reconstruction ([back](#))

PREOPERATIVE

- 1- Patient Education:
 - a. Information on options, risks/benefits, recovery ⁷³⁻⁷⁶
- 2- Fasting & Nutrition:
 - a. Allow clear fluids up to 2 hours before arrival to the hospital and no solid foods after midnight ^{26,77-79}
- 3- Preoperative Analgesics: ²¹ to be given in preop 30 minutes to 2 hours pre-induction
 - a. Gabapentin 600mg po x1 ^{27,80-84}
 - b. Acetaminophen 1000mg po x 1
 - c. Celecoxib 400mg po x 1²¹
 - d. Midazolam 1-4mg IV PRN during nerve block administration only
 - e. Fentanyl 25-100mcg IV PRN during nerve block administration only
- 4- Preoperative anti-emetics: to be given in block room
 - a. Dexamethasone 8mg IV ⁸⁵⁻⁹²
 - i. by Anesthesiologist in block room by slow infusion
- 5- Preoperative Antibiotics: to be given in block room
 - a. Preoperative antibiotics within 60 minutes of incision ⁹³
 - i. by Anesthesiologist in block room
- 6- Regional Anesthesia: Paravertebral block with Pecs I (TPVB+)^{57,94} (Intervention)
 - a. Paravertebral T3/4 block: 0.3% ropivacaine+1:400K epi x 25mL
 - b. Pecs I block with 0.3% ropivacaine with 1:400 epi x 10mL
 - c. TOTAL nerve block LA volume 0.3% ropivacaine x 35 mL = 105mg for 50kg patient

INTRAOPERATIVE

- 1- General Anesthesia
 - a. Induction with Propofol (2-4mg/kg IV), Fentanyl (1-4mcg/kg IV), Rocuronium (0.5-1.2mg/kg IV)
 - b. Endotracheal intubation
 - c. Maintenance with inhalational Sevoflurane (0.6-1.2 MAC)
 - d. Opioid as needed for hemodynamic stability (eg. Fentanyl 0.25-1mcg/kg IV boluses, Hydromorphone to maximum 2mg IV or Morphine to maximum 15mg IV)
 - e. Ondansetron 4mg IV 30 mins before emergence from general anesthesia ^{85,86,88,95}
 - f. Reversal of muscle relaxant at discretion of OR anesthesiologist with Neostigmine or Sugammadex IV
- 2- Sequential Compression Devices & Warming blanket
- 3- Breast block: 18cc of [0.25% bupivacaine with 1:400 000 epinephrine] diluted in 18cc of NS to give total volume of 36cc of [0.125% bupivacaine with 1:400 000 epinephrine] per patient prior to incision

POSTOPERATIVE (POSTANESTHETIC CARE UNIT)

- 1- Celecoxib 200mg po x1 ²¹
- 2- Acetaminophen 1000mg PO q6h ⁹⁶
- 3- Ondansetron 4mg po/IV q6h
- 4- Gravol 25-50mg po/IV q4-6h PRN
- 5- Hydromorphone 0.2-0.4mg IV q5min PRN
- 6- Fentanyl 25mcg – 50mcg IV q15min PRN
- 7- Oxycodone 5mg-10mg po q4h PRN

POSTOPERATIVE (INPATIENT UNIT)

- 1- Celecoxib 200mg po bid for 2 doses ²¹
- 2- Acetaminophen 1000mg PO q6h ⁹⁶
- 3- Ondansetron 4mg po/IV q6h for 72 hours
- 4- Gravol 25-50mg po/IV q4-6h PRN
- 5- Hydromorphone 0.2-0.4mg IV q5min PRN
- 6- Oxycodone 5mg-10mg po q4h PRN
- 7- Gabapentin 200mg po qhs ^{20,21}
- 8- Keflex 500mg po qid for 7 days

PRESCRIPTION (At discharge, as per instructions in Recovery Booklet)

- 1- Tramacet 1 – 2 tablets po q6h (40 tablets) ²¹
 - i. After Tramacet finished, Acetaminophen 500mg po qid
- 2- Celecoxib 200mg po bid for 2 doses ²⁰
 - i. After celecoxib finished: Ibuprofen 400mg po tid ^{20,21}
 - ii. Note: if discharge delayed, order for celecoxib adjusted for a maximum of 2 doses after discharge from PACU
- 3- Gabapentin 200mg po qhs for 2 doses ^{20,21}
 - i. Note: if discharge delayed, order for gabapentin adjusted for a maximum of 2 doses after discharge from PACU
- 4- Ondansetron 4mg po qid for 72 hours
 - i. Note: if discharge delayed, order for ondansetron adjusted for a maximum duration of 72 hours after discharge from PACU
- 5- Keflex 500mg po qid for 7 days
 - i. Note: if discharge delayed, order adjusted to complete a 7-day course

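### Appendices 1 and 2 disagree on Pecs I epinephrine and on block sedation, and the breast-block epinephrine labels in Appendix 2 cannot both hold

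*Protocol*

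**What the plan says.** **Pecs I epinephrine.** Appendix 1, step 3b, specifies "LA Pecs I block: 10ml of 0.3% ropivacaine with 1:400K epinephrine". Appendix 2, Preoperative item 6, is marked as the trial intervention and describes the same 10 mL injection as "Pecs I block with 0.3% ropivacaine with 1:400 epi x 10mL". Item 6a, the line directly above, reads "Paravertebral T3/4 block: 0.3% ropivacaine+1:400K epi x 25mL".

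**Breast block.** Appendix 2, Intraoperative item 3, starts from "18cc of [0.25% bupivacaine with 1:400 000 epinephrine" and has it "diluted in 18cc of NS to give total volume of 36cc of [0.125% bupivacaine with 1:400 000 epinephrine". This is given to each patient before incision.

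**Block sedation.** Appendix 1, step 1, states: "Sedation medication (midazolam 1-2mg and fentanyl 25-50mcg) will be given". Appendix 2, Preoperative item 3, lists "Midazolam 1-4mg IV PRN during nerve block administration only" and, in the same form, fentanyl 25-100 mcg IV as needed.

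**Status of the two appendices.** Quality Control and Assurance names both among the protocols meant to standardize the study interventions. Study Design refers the regional anesthesiologist to Appendix 1 for performing the block. The protocol does not say which appendix prevails where they differ.

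**The concern.** The two appendices are the operative instructions for what is injected and what accompanies it. Where they differ, or where one is internally impossible, the protocol does not define the treatment it intends to standardize.

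The first two items concern the epinephrine content of injected solutions, so the text as it stands is a safety matter. The first affects the composition of the randomized active injection. The second affects background care in both arms.

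The third affects how conduct is classified. A participant who receives no sedation, midazolam 3 mg or fentanyl 75 mcg complies with Appendix 2 and departs from Appendix 1.

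The pilot's design is also that of the planned multi-centre trial, so uncorrected text could be carried to sites that lack this hospital's local practice to fall back on.

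**Working it through.** **Conventions.** A ratio 1:R is 1 g in R mL, that is 1,000,000/R mcg per mL. A solution of p% contains 10p mg per mL. Dilution follows C1 × V1 = C2 × V2. All inputs come from Appendices 1 and 2.

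**Figures that reproduce**
- Total ropivacaine in the study block (Appendix 2, item 6c): 35 mL × 3 mg/mL = 105 mg, as stated.
- Breast-block volume: 18 + 18 = 36 cc, as stated.
- Breast-block bupivacaine: 0.25% × 18/36 = 0.125%, as stated. In mass, 18 mL × 2.5 mg/mL = 45 mg and 36 mL × 1.25 mg/mL = 45 mg.

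**Pecs I epinephrine**
- Appendix 1 (1:400K): 1,000,000/400,000 = 2.5 mcg/mL; × 10 mL = 25 mcg.
- Appendix 2 as written (1:400): 1,000,000/400 = 2,500 mcg/mL; × 10 mL = 25,000 mcg = 25 mg.
- Ratio: 25,000/25 = 1000.
- Whole 35 mL study block: Appendix 1 gives 25 × 2.5 + 10 × 2.5 = 87.5 mcg. Appendix 2 read literally gives 62.5 + 25,000 = 25,062.5 mcg, about 25.06 mg. The ratio is about 286. This restates the same discrepancy over the larger volume and is not a second one.

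**Breast-block epinephrine**
- From the stated start: 18 mL × 2.5 mcg/mL = 45 mcg. In 36 mL this is 1.25 mcg/mL, or 1:800 000.
- From the stated final label: 36 mL × 2.5 mcg/mL = 90 mcg. That would require a start of 90/18 = 5 mcg/mL, or 1:200 000.
- The two labels differ 2-fold in epinephrine content. Saline adds none, so they cannot both hold.

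**Sedation, side by side**

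| | Appendix 1, step 1 | Appendix 2, Preoperative item 3 | Ratio of upper limits |
|---|---|---|---|
| Midazolam | 1-2 mg | 1-4 mg | 4/2 = 2 |
| Fentanyl | 25-50 mcg | 25-100 mcg | 100/50 = 2 |
| Mode | routine | as needed | n/a |

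The stated lower limits agree. As-needed use also permits no dose at all; that is an inference from the wording, not a printed figure.

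**The case against.** **Pecs I.** Three of the four statements of study-block epinephrine read 1:400K, including both in Appendix 1, and a specialist prepares the syringes. On this view the 1000-fold figure measures a misprint, not a likely exposure. That is a fair limit on the practical risk, and it stands. The protocol nevertheless prints two different concentrations for one study injection.

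**Breast block.** This is background care common to both arms, and only the epinephrine label fails. Both points are true. However, Appendix 1 cannot settle the question because it does not describe the breast block. No other passage shows whether the starting or the final label is the one intended.

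**Sedation.** The Appendix 1 ranges lie inside those of Appendix 2, and the wording could describe an initial dose followed by as-needed supplements. The document does not say this. The reading would also leave the permitted total open. If Appendix 2 is added to Appendix 1, the maxima are 2 + 4 = 6 mg and 50 + 100 = 150 mcg. If Appendix 2 is an overall ceiling, they are 4 mg and 100 mcg. Under neither reading does Appendix 1 show that more than 2 mg or 50 mcg is allowed.

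It is also true that the protocol sets no sedation adherence criterion and that the Clinical Form records preoperative medications. What was given will therefore be known. What is missing is a single rule against which to classify it.

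**Weight.** No endpoint, sample size or feasibility criterion depends on these passages. That is accepted and is reflected in the verdict.

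**Conclusion.** The concern holds on all three items.

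- **Pecs I:** as printed, the appendices differ 1000-fold in epinephrine (25 mg against 25 mcg in 10 mL). The likely cause is typographical, and the reference to Appendix 1 limits the practical risk.
- **Breast block:** the starting and final epinephrine labels are incompatible by a factor of 2 (45 against 90 mcg). This is certain from the stated volumes.
- **Sedation:** the appendices differ in mode (routine against as needed) and 2-fold in the upper limit for both drugs.

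The only assumptions are the usual reading of a 1:R ratio as grams per millilitre and a diluent free of epinephrine. No bias in the comparison between arms is claimed. The point should be fixed because the passages are operative drug instructions with a safety bearing and correction costs almost nothing.

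**What to change.** The investigators and the anesthesiology team should check the three passages against intended practice and amend the protocol so that:

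1. the Pecs I epinephrine concentration is stated in one place, and the other appendix refers to it;
2. the breast-block starting solution, diluent and final concentration agree arithmetically for both bupivacaine and epinephrine;
3. the block-sedation instruction (routine or as needed, and its range) is stated once and cross-referenced.

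A sentence saying which appendix prevails in case of conflict would guard against recurrence. Which concentration, dilution or sedation rule is right is for the clinical team, and none is proposed here. The cost is a text correction in a minor amendment, with no extra patients or procedures.
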